8.6.2 Assessment of laboratory abnormalities

For every laboratory assessment, the investigator will evaluate if the lab test is normal or abnormal. If abnormal, the investigator will assess if this finding is clinically significant or not. If a lab parameter is abnormal and clinically significant, it should be reported as an adverse event (AE).

Please also note that an abnormal test must be compared with the previous value. An AE is a new event after the administration of the 1st dose of the study drug or a worsening in the condition (in the case of lab tests, increase in severity by CTCAE v4.03 which is judged clinically significant by the investigator).

Laboratory abnormalities should be assessed as "clinically significant" (and therefore have to be reported as an AE) only if they meet AT LEAST ONE of the following conditions:

- The abnormality suggests a disease and/or organ toxicity AND this abnormality was not present at the screening visit or is assessed as having evolved since the screening visit
- The abnormality results in discontinuation of the study drug
- The abnormality requires medical intervention or concomitant therapy

Lab parameters which are classified with regards of severity as CTCAE v4.03 Grade 3 or Grade 4 must be carefully assessed, as they are likely to require medical intervention and/or be life-threatening in terms of severity.

For the purpose of this protocol, all **clinically significant** Grade 3 and Grade 4 lab abnormalities must be reported as an AE.

Furthermore, lab abnormalities associated with clinical signs and symptoms will also be considered clinically significant. When reporting an abnormal lab as an adverse event, a clinical diagnosis should be recorded rather than the abnormal value itself, if available. However, in these cases, the adverse event should be recorded as the syndromic clinical diagnosis (ex. acute pancreatitis instead of each finding separately: high levels of amylase, high levels of lipase, abdominal pain and vomiting; Ex "hypokalemia" rather than "decreased potassium levels").

8.6.3 Serious Adverse Event

An adverse event will be defined as serious if it results in one or more of the following:

• results in death,

i.e. causes or contributes to the death.

• is life-threatening,

in this context refers to an AE/AR in which the patient was at risk of death at the time of the AE/AR; it does not refer to an AE/AR that hypothetically might have caused death if more severe.

• requires in-patient hospitalization or prolongs existing hospitalization,

i.e. the AE requires at least an overnight admission or prolongs a hospitalisation beyond the expected length of stay.

- Hospital admissions or prolongation of hospitalisation for an elective surgery planned before study entry, for social reasons and/or financial reasons, for any elective surgery (i.e. plastic surgery) or for normal disease management (including treatment adjustment) are NOT to be considered as a SAE according to this criterion (i.e. if the protocol or the standard management of the disease under study requires planned hospitalisation).
- results in persistent or significant disability or incapacity,
- is a congenital anomaly/birth defect,

i.e. an adverse event outcome in a child or foetus of a subject exposed to the Investigational Medicinal Product (or marketed medicinal product) before conception or during pregnancy.

• is an important medical event, i.e. medically significant.

Medical and scientific judgment should be exercised in deciding whether other situations should be considered serious events/reactions, such as important medical events that might not be immediately life threatening or does not directly result in death or hospitalization, but which might jeopardize the patient or might require intervention to prevent one of the other outcomes listed above.

What is not an SAE?

In this study, the patient may be hospitalized for receiving Ambisome[®] treatment, with discharge expected on D16. This hospitalization for receiving treatment to participate in the study will NOT be considered as a SAE.

Similarly, hospitalization or prolongation of hospitalization for standard PKDL disease management will NOT be considered as a SAE.

Any prolongation of the hospitalization that is not related to a medical event but related to any social and/or financial reasons and/or an elective planned surgery, will NOT be considered as an SAE.

SAE onset date:

SAE onset date is the SAE start date or date a pre-existing AE becomes serious.

8.6.4 Adverse Event of Special Interest

Adverse event of special interest (AESI) is an adverse event (serious or non-serious) of scientific and medical concern by the Sponsor, for which monitoring and rapid communication by the investigator to the Sponsor may be appropriate.

For this study, allergic reactions to Ambisome[®] or infusion related reactions occurring during test dose or during study drug administration resulting in treatment discontinuation will be considered AESI.

Severe Test Dose Reaction: If during administration of test dose, severe anaphylactic reaction occurs, then Ambisome[®] infusion should be immediately discontinued and patients should not receive further infusions of Ambisome[®]. These severe anaphylactic reactions should be

reported as serious Adverse Event of Special Interest (AESI).

8.6.5 Eliciting Adverse Event information

The investigator is required to report all directly observed adverse events and all adverse events spontaneously reported by the trial subject using concise medical terminology. In addition, each trial subject will be questioned about the occurrence of adverse events at each study visit (scheduled and non-scheduled) since the time of the last study visit, as well as follow-up from previously recorded adverse event up to 24 months.

8.6.6 Adverse Event reporting period

All adverse events that occur during the adverse event reporting period specified below must be reported to DNDi.

The adverse events reporting period for this trial will be as follows:

Non-serious adverse events: All AEs (related or unrelated) will be reported upon administration of the first dose of trial medication until the 6-months follow-up visit. Furthermore, AEs judged related to study procedures that occur during the screening period (from signature of the informed consent) will also be reported.

Non-serious AEs that occur between 6 months and 24 months visit that are judged as related to the study drug or study-related will be reported.

Serious adverse events: All SAEs must be reported upon subject enrolment in the trial (signature of the informed consent) until the end of the subject participation in the trial (including post-treatment follow-up period 24 Month).

For 24 months follow-up visit: for patients who have already completed the 12 months visit and consented for the 24 months follow-up visit, the complete history of signs and symptoms since the 12 months visit will be recorded, including medications that could affect the treatment outcome (*e.g.* immunomodulators), any other medications and adverse events that may have occurred during this period. Adverse events that fulfil the criteria of seriousness will be reported within 24hs of knowledge of the event, following the reporting requirements as described below and AEs assessed as related to the previous study treatment or study-related will be collected too.

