2.2 Study Endpoints

2.2.1 Primary Endpoint

Efficacy:

 To measure the efficacy (definitive cure at 12 months) of two treatment regimens in subjects with PKDL according to clinical criteria: complete resolution of papular and nodular lesions (flattening of 100% of lesions) and significant improvement (> 80% repigmentation) of macular lesions by 12 months after the end of treatment.

Safety:

• To assess the safety of the two regimens (SAEs, AESI and frequency and severity of AEs) from the start of treatment through the 12--month follow-up period and 24 months study visit.

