10.2 Summary of analyses

Descriptive statistics will be used to present study data. Continuous variables will be presented as number of observations (n), mean, standard deviation (SD), median, minimum and maximum values. Categorical variables will be presented as counts and percentages.

Median time to the development of any AE will be determined using life-table analysis. All data will be presented separately by treatment group, local and systemic AEs. AEs and medical history will be coded using the most recent version of the Medical Dictionary of Regulatory Activities (MedDRA) preferred terms and will be grouped by system, organ, and class (SOC) designation.

Protocol number: DNDi-MILT COMB-01-PKDL

Protocol Version/Date: V3.0, 25 Feb 2020

Concomitant medications will be coded using the most recent version of WHO drug Dictionary.

Summary statistics will be provided by group including the frequency, severity, seriousness and relationship of AEs to each study drug organized by preferred term by SOC grouping.

Efficacy endpoints will be presented as summary statistics by treatment group and will be conducted once all subjects complete their initial cure assessment visit and the 12-months visit. The number of subjects who met the criteria for cure divided by the total number of subjects in that group will be presented by study group, and the correspondent 95% confidence interval. In addition, secondary efficacy endpoints will be described for the 24-months follow-up visit.

Subjects who are lost to follow-up will be compared to those completing the study with respect to study site, demographic, and clinical factors. If lost to follow-up exceeds 20% of the sample, attempts will be made to seek out these dropouts (or their proxies) to ascertain final outcomes. The attributes of people that are found through this process will be compared to those not lost to follow up.

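### The primary safety endpoint covers all AEs to months 12 and 24, but unrelated non-serious AEs are reportable only to month 6, so all-AE frequency beyond month 6 cannot be obtained as worded

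*Protocol*

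**What the plan says.** **Endpoint.** Protocol 2.2.1, and the synopsis in the same terms, make safety a primary endpoint made up of SAEs, AESIs and "frequency and severity of AEs) from the start of treatment through the 12--month follow-up period and 24 months study visit". No part of it is restricted by causality or seriousness.

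**Collection.** Section 8.6.6 sets three tiers:
- Non-serious events to month 6: "All AEs (related or unrelated) will be reported upon administration of the first dose of trial medication until the 6-months follow-up visit".
- Non-serious events after month 6: "Non-serious AEs that occur between 6 months and 24 months visit that are judged as related to the study drug or study-related will be reported".
- For SAEs the rule reads: "All SAEs must be reported upon subject enrolment in the trial (signature of the informed consent) until the end of the subject participation", with the 24-month follow-up included.

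The safety row of the schedule of events is only partly legible, but it also appears to be tiered by period.

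**Wider wording elsewhere.** Section 8.6.5 asks the investigator to report every AE that is observed or volunteered, and adds that "each trial subject will be questioned about the occurrence of adverse events at each study visit (scheduled and non-scheduled" (the sentence goes on to follow-up of earlier events to 24 months). It sets no relatedness limit. The last paragraph of 8.6.6, on patients already past the 12-month visit, first calls for AEs since that visit to be recorded. It then returns to serious events and related AEs.

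**Analysis.** Section 10.2 states: "Median time to the development of any AE will be determined using life-table analysis". It gives no time window and no censoring time. Section 10.7 plans the proportion with at least one treatment-emergent AE and tables by severity and causality, again with no window.

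**The concern.** The endpoint and the data meant to supply it cover different periods. Up to the 6-month visit every non-serious AE counts. After it, a non-serious AE enters the database only if an open-label investigator attributes it to the drug or to the study. A table headed as AE frequency through 24 months would join two kinds of ascertainment under one label, and the total would be too low.

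The analysis sections do not prevent this. With no window in 10.2 or 10.7, a programmer who follows the endpoint would take 24 months as the horizon. Patients would then stay in the risk set of the life table for events that no longer have to be reported. A later analysis plan can set a censoring time, but it cannot recover events that sites were never asked to report.

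The inconsistency between 8.6.5 and 8.6.6 adds a second difficulty. One site could report every AE after month 6 and another only the related ones, and each could point to the protocol.

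**Working it through.** **1. Windows side by side** (2.2.1 against 8.6.6 and 8.6.4)

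| Component | Endpoint window | Reportable window | Match |
|---|---|---|---|
| SAEs | to 24 months | consent to 24 months | yes |
| AESIs | to 24 months | by definition arise at the test dose or drug administration | yes |
| Related non-serious AEs | to 24 months | first dose to 24 months | yes |
| Unrelated non-serious AEs | to 24 months | first dose to 6-month visit | **no, after month 6** |

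The gap is one cell: unrelated non-serious AEs after month 6.

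**2. Calendar time**

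- To month 12: full ascertainment 6/12 = 50%; not full (12 − 6)/12 = 50%.
- To month 24: full ascertainment 6/24 = 25%; not full (24 − 6)/24 = 75%.

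These are shares of time, not of events.

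**3. Can the life table be computed?** Yes, with patients censored at the 6-month visit. Its median is then estimable if at least half of the patients have an AE by that visit. The protocol gives no AE rate, so take F6, the share with any AE by month 6, as an assumption, with constant hazard:

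median = 6 × ln 2 / (−ln(1 − F6))

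| Assumed F6 | Median (months) | Reached by month 6? |
|---|---|---|
| 80% | 2.6 | yes |
| 60% | 4.5 | yes |
| 50% | 6.0 | just |
| 40% | 8.1 | no |
| 30% | 11.7 | no |
| 20% | 18.6 | no |

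**4. What if follow-up runs to month 24 uncensored?** Let u be the assumed share of the AE hazard that is unrelated and non-serious, which drops out after month 6.

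true F24 = 1 − (1 − F6)^4

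apparent F24 = 1 − (1 − F6) × (1 − F6)^(3(1 − u))

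The exponent 3 is the 18 months after month 6 divided by 6. With F6 = 30%, true F24 = 1 − 0.7^4 = 76%.

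| u | Apparent F24 at F6 = 30% |
|---|---|
| 30% | 1 − 0.7 × 0.7^2.1 = 67% |
| 60% | 1 − 0.7 × 0.7^1.2 = 54% |
| 90% | 1 − 0.7 × 0.7^0.3 = 37% |

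With F6 = 60% the true value is 97%, and the apparent values are 94%, 87% and 70%. The direction is fixed, but the size depends on F6 and u, which the protocol does not supply.

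**The case against.** The best defence is that the tiering is sensible and little is lost. Ambisome ends on day 15 and miltefosine on day 21, with up to day 24 allowed after an interruption. All AEs are therefore collected for more than five months after the last dose. SAEs of any cause and related AEs continue to 24 months. What is missing is the part least informative about drug safety. Section 10.7 is framed around treatment-emergent AEs, whose window is normally set in an analysis plan. The trial is non-comparative, so a causality filter distorts no formal comparison between arms. All of this stands, and it limits the weight of the point. It does not make the wording of 2.2.1 agree with 8.6.6.

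Four stronger readings are tempting, and the documents do not support them:

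- *The life table cannot be computed.* Section 10.2 gives it no 12- or 24-month horizon, and it works with censoring at month 6. Its silence on censoring is not a rule that patients stay at risk, and that detail may belong in an analysis plan.
- *Half or three quarters of AEs are lost.* Those fractions describe calendar time. The protocol gives no AE rate over time.
- *The definition of an AE changes at month 6.* The definition in 8.6.1 is constant; only what must be reported changes.
- *Late unrelated events certainly go unrecorded.* Section 8.6.5 and the 24-month paragraph of 8.6.6 leave this open. Events may be noted at site without being reportable, which is why the two sections need reconciling.

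**Conclusion.** The point holds in a limited form. For unrelated non-serious AEs after the 6-month visit, the primary safety endpoint asks for data that 8.6.6 does not require. Frequency and severity of all AEs through month 12 or 24 cannot be delivered as worded, and a pooled figure presented as such would be too low by an unknown amount. Every other component of the endpoint is covered to 24 months, and all AEs are covered to month 6.

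The mismatch rests on the text alone and needs no assumption. The illustrated under-count (76% true against 37% to 67% apparent at F6 = 30%) rests on a constant hazard and on assumed values of F6 and u. It shows only that the effect could be material. The collection rule is also inconsistent between 8.6.5 and 8.6.6, so late AE counts could partly reflect site practice.

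**What to change.** 1. In 2.2.1 and the synopsis, restate the safety endpoint as the frequency and severity of all AEs from first dose to the 6-month visit, plus SAEs, AESIs and drug- or study-related AEs to 24 months.
2. In 10.2, state that the analysis of time to any AE is censored at the 6-month visit, and that the median is reported as not reached if fewer than half of the patients have had an AE by then.
3. In 10.7, tabulate 0-6 months and 6-24 months separately, and label the second period as SAEs and related AEs only.
4. Reconcile 8.6.5 and the 24-month paragraph of 8.6.6 with the tiered rule, so that all sites report the same events after month 6.

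The cost is wording and one extra table split, with no new data. The price is a narrower stated safety endpoint. The alternative, extending reporting of all AEs to 24 months, would need additional collection. It could be only partly retrospective, because the schedule's footnote on the 24-month visit allows for patients who had already reached that point before this amendment was approved.

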8.6.7 Adverse Event reporting requirements

Information on adverse events must be evaluated by a physician. Each adverse event is to be classified by the investigator as serious or non-serious (based on the criteria mentioned in 8.7.3). This classification will determine the reporting procedure for the event to DNDi and Health Authorities/Ethics Committees (as per local regulatory requirements).

All serious adverse events (SAE) are to be reported immediately (within 24 hours of occurrence of SAE by the investigator) to DNDi (on [contact]), regulatory authorities, and Institutional Ethics Committee, as per local regulations, using the SAE report form. This includes a description of the event, onset date and seriousness criteria, duration, severity, relationship to study drugs, outcome, measures taken and all other relevant clinical and laboratory data. The initial report is to be followed by submission of additional information (follow-up SAE form) as it becomes available within required timelines as per local regulations to regulatory authorities, to Ethics Committee where the trial has been conducted.

In the situation where an AESI fulfils the criteria of a serious AE, this information will be captured in the AESI form and reported to the DNDi clinical team as per instructions below. There is no need to complete an SAE form because the AESI form contains all necessary information pertaining to the SAE and additional AESI sections.

The PI and sponsor must ensure that all Sponsor reviewed SAEs (CIOMS report) are reported to the regulatory authorities and Institutional Ethics Committee within the allocated timeframe as per current regulatory guidelines, as described above.

Serious adverse events should also be reported on the clinical trial adverse event case report form (CRF). It should be noted that the form for reporting of SAE (SAE form) is not the same as the adverse event section of the CRF. Where the same data are collected, the two forms must be completed in a consistent manner, and the same medical terminology should be used.

All AESI are to be reported immediately (within 24 hours of awareness of the AESI by the investigator) to the DNDi clinical team (on [contact]), using the AESI report form. This includes a description of the event, onset date and type, duration, severity, relationship to study drug, outcome, measures taken and all other relevant clinical and laboratory data. The initial report is to be followed by submission of additional information (follow-up AESI form) as it becomes available. Any follow-up reports should be submitted as soon as possible and if possible within 5 working days. AESI will be transmitted to the primary PV contact (and back-up) and the PV Team Leader via email.

If serious, these AESI reports will be transmitted by the clinical team to DNDi PV team (as any other SAE at [contact]). The Investigator should follow the regular process of reporting SAE to the local authorities and Ethics Committee.

AESI are also to be reported in the clinical trial adverse event case report form (CRF).

Non-serious AESIs **do not** need expedite submission to the Ethics Committee. These will be reported to the DSMB and in the regular periodic report, as per local regulations.

Non-serious adverse events are to be reported on the CRF, including description of the event, onset date, duration, severity, seriousness, relationship to study drugs, actions taken and outcome. In the CRF, a given adverse event will be recorded only one time per patient, and the severity recorded will be the maximum level reached. If several distinct episodes of the same condition occur, their number will be recorded in the CRF.

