8.6.9 Adverse Event causality assessment

For each serious and non-serious adverse events, the investigator is required to assess if there is a causal relationship between the adverse event and the study drugs, i.e. to determine whether **there is at least a reasonable possibility** that one of both study drugs caused or contributed to the adverse event. This means that there are facts and arguments to suggest a causal relationship.

To help investigators with the decision binary tree in the evaluation of causality, the CIOMS VI group recommends that investigators be asked to consider the following before reaching a decision:

- Medical history
- Lack of efficacy/worsening of existing condition
- Study medications
- Other medications (concomitant or previous)
- Withdrawal of study medication, especially following trial discontinuation / end of study medication
- Erroneous treatment with study medication (or concomitant)
- Protocol related procedure

Using this information, the investigator will classify each adverse event as:

- **Not related:** There is no reasonable possibility of causal relationship between an AE and study drug
- **Related:** There is at least a reasonable possibility of a causal relationship between an AE and a study drug. This means that there are **facts** (evidence) or arguments to suggest a causal relationship.

The decision to suspend, and resume treatment or to permanently interrupt treatment due to an adverse event will be left to the clinician in charge.

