10.7 Safety Analysis

All patients enrolled and who have been started on study medication will be included in the safety analysis (treatment-emergent AEs). The AE and medical history data will be coded using MedDRA dictionary.

AE's will be tabulated by System Organ Class (SOC), severity (based on the CTCAE v4.03 see section 8.7.7), seriousness and by causal relationship to study drugs.

The proportion of patients with SAE, AESI and/or AEs leading to treatment discontinuation will be described per System Organ Class (using preferred terms defined by MedDRA) and summarised according to relationship to treatment and severity (CTCAE, version 4.03). In addition, a narrative for each of the SAE, AESI and AE leading to treatment discontinuation will be developed describing all aspects of the medical event.

The proportion of patients presenting at least one treatment emergent AE (TEAE) will be presented. All TEAEs will be described per study arm using the same classification as presented above. AEs will be tabulated by severity (CTCAE V4.03) and causality.

Abnormalities of laboratory/procedures results will be tabulated with respect to clinical significance. In addition, shift tables and graphs will be generated to describe the laboratory parameter values over time, per treatment arm.

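### Section 8.6.7 stores one CRF record per adverse event per patient at its worst grade, with no rule for which episode supplies causality, seriousness or onset, so severity and relationship summaries can mismatch

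*Protocol*

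**What the plan says.** Section 8.6.7 lists what the CRF holds for a non-serious adverse event: a description, then "onset date, duration, severity, seriousness, relationship to study drugs, actions taken and outcome". It goes on: "a given adverse event will be recorded only one time per patient, and the severity recorded will be the maximum level reached". The following sentence deals with recurrence: "If several distinct episodes of the same condition occur, their number will be recorded in the CRF". The rule therefore covers separate episodes as well as the peak of one continuous event.

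Other sections rely on these records:

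- Section 8.6.9: "For each serious and non-serious adverse events, the investigator is required to assess if there is a causal relationship". The answer is related or not related.
- Section 10.2: "Summary statistics will be provided by group including the frequency, severity, seriousness and relationship of AEs to each study drug".
- Section 10.7: "AEs will be tabulated by severity (CTCAE V4.03) and causality". The same section also summarises the proportion of patients with SAEs, AESIs or AEs leading to discontinuation by relationship and severity.
- Section 2.2.1 makes the frequency and severity of AEs part of the primary safety endpoint.
- Section 8.6.6 collects all non-serious AEs from first dose to the 6-month visit. After that it collects only those judged related to study drug or to the study.

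**The concern.** A record that merges several episodes carries one grade, one causality, one seriousness and one onset. The protocol fixes the grade (the maximum) and leaves the rest to whoever completes the form. A mild episode judged related during treatment and a severe one judged unrelated before the 6-month visit can end up as a single severe, related event. In the reverse case, a severe related event can be stored as not related. Sites may also resolve the choice differently.

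Recurrence is foreseeable. Section 4.2 itself refers to how common vomiting and diarrhoea are with miltefosine, and both arms receive five infusions. In the combination arm the last infusion is on D15 and miltefosine runs to D21, so attribution to each drug can differ between early and late episodes of one condition.

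This is a data-collection rule. Worst-grade summaries can always be derived from episode-level data. Episode-level data cannot be rebuilt from a merged record, so an analysis plan cannot repair it for ordinary non-serious events.

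**Working it through.** The protocol states no figure to reproduce on this point. The check is textual, followed by an illustration under assumed inputs.

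**Step 1: which attributes have a merging rule.** Of the seven attributes in the Section 8.6.7 list, severity has one (the maximum). Onset, duration, seriousness, relationship, action and outcome have none. The number of episodes is kept as a count.

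**Step 2: apply each possible causality rule.** Take one patient with two distinct episodes of the same condition, both non-serious and both before the 6-month visit. The first is grade 1 and related; the second is grade 3 and unrelated. The correct worst grades are 3 (all-cause) and 1 (related).

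| Causality taken from | Stored record | All-cause worst grade | Related worst grade |
|---|---|---|---|
| First episode | grade 3, related | 3, correct | 3, wrong |
| Any episode related | grade 3, related | 3, correct | 3, wrong |
| Worst-grade episode | grade 3, not related | 3, correct | none; the grade 1 event is lost |

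The all-cause column is right under every rule. No rule gets the related column right, because one record cannot hold two grades. The third rule does store a true combination (grade 3 and unrelated is what happened) but drops the milder related episode.

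Reverse the causalities: first episode grade 1 and unrelated, second grade 3 and related. The first-episode rule now stores grade 3, not related, which hides a related grade 3 event. The other two rules store it correctly.

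**Step 3: how often the stored causality could miss the worst-grade episode.** These inputs are assumptions, not protocol figures. There are two episodes per record with independent causality; q1 and q2 are the probabilities that the first and second are related; h is the probability that the second is the worse one.

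- Episodes differ in causality: d = q1(1 − q2) + (1 − q1)q2.
- First-episode rule mismatches: h × d.
- Any-related rule mismatches (stored as related, worst episode unrelated): (1 − h)(1 − q1)q2 + h × q1(1 − q2).

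| q1, q2 | h | d | First-episode rule | Any-related rule |
|---|---|---|---|---|
| 0.9, 0.1 | 0.25 | 0.82 | 0.205 | 0.21 |
| 0.9, 0.1 | 0.50 | 0.82 | 0.41 | 0.41 |
| 0.7, 0.3 | 0.25 | 0.58 | 0.145 | 0.19 |
| 0.7, 0.3 | 0.50 | 0.58 | 0.29 | 0.29 |
| 0.5, 0.5 | 0.25 | 0.50 | 0.125 | 0.25 |
| 0.5, 0.5 | 0.50 | 0.50 | 0.25 | 0.25 |

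First row in full: d = 0.9 × 0.9 + 0.1 × 0.1 = 0.82. First-episode rule: 0.25 × 0.82 = 0.205. Any-related rule: 0.75 × 0.1 × 0.1 + 0.25 × 0.9 × 0.9 = 0.0075 + 0.2025 = 0.21.

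These are shares of two-episode records only. Single-episode records, and records whose episodes share the same causality, have no mismatch.

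**The case against.** The strongest case is that worst grade per patient plus an episode count is a deliberate, workable rule for a non-comparative, descriptive trial, and that much detail survives elsewhere. Most of the supporting points stand:

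- SAEs and AESIs have their own forms with onset, severity and relationship (Section 8.6.7). Infusion or allergic reactions that end treatment are AESIs (Section 8.6.4); milder reactions are not.
- Serial potassium values remain in the laboratory data, and Section 10.7 plans shift tables and graphs over time.
- Section 7.2 has all vomiting episodes recorded in the setting of post-dose observation, though it does not give each one a grade or causality.
- The laboratory guidance in Section 8.6.2 prefers a syndromic diagnosis to separate symptoms. A later infection with vomiting would most naturally be its own record and would not be merged with vomiting on miltefosine.
- After 6 months unrelated non-serious events are no longer collected, so the mixing is largely an early one.
- Section 10.7 does not say that severity and causality are crossed. If they are tabulated separately, the severity table at maximum grade is valid.
- Median time to any AE needs only the first onset and is unaffected if that is the onset stored, although the protocol does not say so.

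A reader might also infer that the SAE form and the CRF must give conflicting dates. The text does not show this. It foresees a later date for the serious phase ("SAE onset date is the SAE start date or date a pre-existing AE becomes serious"), asks for consistency where both forms collect the same data, and states the one-record rule directly after a sentence on non-serious events.

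These points narrow the problem. They do not supply the missing rule, and they do not restore per-episode grade and causality for ordinary non-serious events.

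**Conclusion.** The point holds in limited form. The gap in Section 8.6.7 is real and touches a component of the primary safety endpoint. Its effect is confined to patients with repeat episodes of the same condition that differ in grade and causality, and to events without their own SAE or AESI form. For those patients the severity and relationship summaries can pair the worst grade with the wrong causality, and no rule applied to a single record gives correct all-cause and related worst grades in every case.

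The frequency in this trial cannot be derived, because the protocol gives no rate of repeat episodes. The range of 12.5% to 41% of two-episode records rests wholly on the assumed probabilities and on independent causality between episodes.

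A reader might go further and infer that the tables will be wrong, that AE durations will be inflated, or that episodes will be counted at the stored grade. The documents do not support this. Error needs discordant repeat episodes, no analysis of AE duration is planned, and nothing in the protocol multiplies episode count by grade.

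**What to change.** Amend Section 8.6.7 so that each distinct episode is its own CRF line with onset, end, grade, seriousness, causality and action. Derive the worst grade per patient and preferred term only at analysis, once for all-cause events and once for related events. The worst-grade tables can still be produced. The cost is a wording change in the CRF instructions and more AE lines for patients with repeated episodes.

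If data collection is too advanced for that, state in Section 8.6.7 that causality and seriousness follow the worst-grade episode and that onset follows the first. This makes the stored grade and causality a true pair and keeps time to first AE usable. It has two limits that should be stated with the tables: milder related episodes drop out of the related summaries, and the stored onset may not belong to the stored grade.
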